## 10.3. Appendix 3: Study Phases and Treatment Emergent Adverse Events

### 10.3.1. Study Phases

Since participants are on Relvar/Breo study treatment from the time they enter run-in, assessments and events will be classified according to time of occurrence relative to the randomisation date and last stop date of Relvar/Breo treatment. The randomisation and latest exposure treatment stop dates will be used to determine whether an assessment or event was during pre-screening treatment, run-in treatment, on-treatment or post-treatment. If it is not possible to tell whether an assessment or event was on-treatment or not, it will be considered as on-treatment.

#### 10.3.1.1. Study Phases for Concomitant Medication

A medication will be summarised in every study phase (pre-screening, run-in, on- or post-treatment) in which it was taken, so a medication that was started during the run-in period and stopped during the post-randomisation treatment period will appear in both the run-in-treatment and the on-treatment summaries.

On-treatment will be considered to be from the day of randomisation to treatment arm until the last (Relvar/Breo) treatment stop date. Post-treatment will be considered to be from the day after the last treatment stop date and onward. Run-in-treatment will be considered from the screening visit until prior to randomisation to treatment arm date. If a participant's last treatment stop date is missing, this will be assumed to be the date of the last recorded on-treatment visit up to Visit 10 (not including the Follow-up visit) or the return of the last Relvar/Breo container, whichever is later.

Study Phase	Definition
Pre-Screening Treatment	Date of Medication < Screening Visit Date
Run-in Treatment	(Date of Medication $\geq$ Screening Visit date) and (Date of Medication < Randomisation Date)
On-Treatment	(Date of Medication $\geq$ Randomisation Date) and (Date of Medication $\leq$ Last Treatment Stop Date)
Post-Treatment	Date of Medication $>$ Last Treatment Stop Date

#### 10.3.1.2. Study Phases for Asthma Exacerbations

Study Phase	Definition
Run-in-Treatment	(Exacerbation Onset Date $\geq$ Screening Visit date) and (Exacerbation Onset Date < Randomisation Date)
On-Treatment	(Exacerbation Onset Date $\geq$ Randomisation Date) and (Exacerbation Onset Date $\leq$ Last Treatment Stop Date)+1
Post-Treatment	Exacerbation Onset Date $>$ Last Treatment Stop Date+1

### 10.3.1.3. Treatment Emergent Flag for Adverse Events

Study Phase	Definition
Run-in-Treatment*	(AE Start Date $\geq$ Screening Visit date) and (AE Start Date $<$ Randomisation Date)
On-Treatment	(AE Start Date $\geq$ Randomisation Date) and (AE Start Date $\leq$ Last Treatment Stop Date)+1
Post-Treatment	AE Start Date $>$ Treatment Stop Date + 1
Onset Time Since First Dose (days)*	
Time Since First Dose will be derived as follows:
 
 
• If Randomisation Date or AE Onset Date are missing => missing
 
• If Randomisation Date <math>></math> AE Onset Date then => AE Onset Date – Randomisation Date
 
• If Randomisation Date <math>\leq</math> AE Onset Date then => AE Onset Date – Randomisation Date + 1
 

\*For participants who enter the run-in treatment phase but do not get randomised, use the last run-in date instead of randomisation date for the “Run-in-Treatment” phase and “Onset Time Since First Dose (days)” as the participants would not have a randomisation date.

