### **5.2. Number of Subjects**

Approximately 600 subjects will be screened to achieve 432 randomised and 380 subjects are anticipated to have data available for the primary analysis for an estimated total of 76 subjects per treatment group.

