## 4. ANALYSIS POPULATIONS

Population	Definition / Criteria	Analyses Evaluated
All participants	
 
• All participants who signed the ICF
 
	Study Population
Screened	
 
• All participants who were screened for eligibility.
 
	Study Population
Enrolled	
 
• All participants who passed screening and entered the study. Included are: Run-in Failures; Randomized Participants
 
 
Note screening failures are excluded from the Enrolled population as they did not enter the study.
	Study Population Safety
Randomized	
 
• All participants who were randomly assigned to a treatment arm in the study.
 
• This population will be based on the treatment arm the participant was randomised to.
 
	Study Population
Intent-To-Treat (ITT)	
 
• The ITT population comprises all randomised participants, excluding those who were randomised in error. A participant who is recorded as a screen or run-in failure but is randomised, and does not receive a dose of study treatment, is considered to have been randomised in error. Any other participant who received a randomisation number will be considered to have been randomised.
 
• This population will be based on the treatment arm the participant was randomised to.
 
	Study Population Efficacy (ELLIPTA Adherence, Rescue Medications Use, PRO, PEF and FeNO) Safety

Refer to Section [10.8 Appendix 8](#): List of Data Displays which will detail the population used for each display.

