#### 10.8.8. Safety Tables

Safety: Tables					
No.	Population	IDSL / Example Shell	Title	Programming Notes	Deliverable [Priority]
Adverse Events (AEs)					
3.1.	ITT	SAFE_T1	Overview of On-Treatment and Post-Treatment Non-Serious AEs leading to Withdrawal, Non-Serious ADRs and SAEs	Include total column	SAC [2] DRY RUN [1]
3.2.	ITT	SAFE_T1	Overview of Run-In Treatment Non-Serious AEs leading to Withdrawal, Non-Serious ADRs and SAEs	Include total column	SAC [2] DRY RUN [1]

Safety: Tables					
No.	Population	IDSL / Example Shell	Title	Programming Notes	Deliverable [Priority]
3.3.	Not in ITT	SAFE_T1	Overview of Run-In Treatment Non-Serious AEs leading to Withdrawal, Non-Serious ADRs and SAEs for Subjects not in ITT	Total column only	SAC [2] DRY RUN [1]
3.4.	ITT	IDSL_AE15	Summary of Common (>=1%) Non-serious Adverse Events by System Organ Class and Preferred Term (Number of Subjects and Occurrences)	Include total column. Do not apply rounding.  Footnote: Non-serious Adverse Events includes non-serious ADRs and non-serious AEs leading to withdrawal  Disclosure table.	SAC [2] DRY RUN [1]
3.5.	ITT	IDSL_AE15	Summary of Common (>=1%) Run-In Treatment Non-Serious Adverse Events by System Organ Class and Preferred Term (Number of Subjects and Occurrences)	Include total column only. Do not apply rounding.  Footnote: Non-serious Adverse Events includes non-serious ADRs and non-serious AEs leading to withdrawal  Disclosure table.	SAC [2] DRY RUN [1]
3.6.	Not in ITT	IDSL_AE15	Summary of Common (>=1%) Run-In Treatment Non-Serious Adverse Events by System Organ Class and Preferred Term (Number of Subjects and Occurrences) for Subjects not in ITT	Include total column only. Do not apply rounding.  Footnote: Non-serious Adverse Events includes non-serious ADRs and non-serious	SAC [2] DRY RUN [1]

Safety: Tables					
No.	Population	IDSL / Example Shell	Title	Programming Notes	Deliverable [Priority]
				AEs leading to withdrawal Disclosure table.	
Adverse Drug Reactions (ADRs)					
3.7.	ITT	IDSL_AE1	Summary of On-Treatment Adverse Drug Reactions	Include total column. All ADRs (Non-serious and Serious)	SAC [2] DRY RUN [1]
3.8.	ITT	IDSL_AE1	Summary of Post-Treatment Adverse Drug Reactions	Include total column. All ADRs (Non-serious and Serious)	SAC [2] DRY RUN [1]
3.9.	ITT	IDSL_AE1	Summary of On-Treatment Serious Adverse Drug Reactions	Include total column	SAC [2] DRY RUN [1]

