3.10.	ITT	IDSL_AE1	Summary of Post-Treatment Serious Adverse Drug Reactions	Include total column	SAC [2] DRY RUN [1]
3.11.	ITT	IDSL_AE1	Summary of On-Treatment Non-Serious Adverse Drug Reactions	Include total column	SAC [2] DRY RUN [1]
3.12.	ITT	IDSL_AE1	Summary of Post-Treatment Non-Serious Adverse Drug Reactions	Include total column	SAC [2] DRY RUN [1]

Safety: Tables					
No.	Population	IDSL / Example Shell	Title	Programming Notes	Deliverable [Priority]
Serious Adverse Events (SAEs)					
3.13.	ITT	IDSL_AE16	Summary of Serious Adverse Events by System Organ Class and Preferred Term (Number of Subjects and Occurrences)	Include total column	SAC [2] DRY RUN [1]
3.14.	ITT	IDSL_AE16	Summary of Run-In Treatment Serious Adverse Events by System Organ Class and Preferred Term (Number of Subjects and Occurrences)	Include total column	SAC [2] DRY RUN [1]
3.15.	Not in ITT	IDSL_AE16	Summary of Run-In Treatment Serious Adverse Events by System Organ Class and Preferred Term (Number of Subjects and Occurrences) for Subjects not in ITT	Include total column	SAC [2] DRY RUN [1]
3.16.	ITT	IDSL_AE1	Summary of On-Treatment Serious Adverse Events	Include total column	SAC [2] DRY RUN [1]
3.17.	ITT	IDSL_AE1	Summary of Post-Treatment Serious Adverse Events	Include total column	SAC [2] DRY RUN [1]
Adverse Events leading to Withdrawal					
3.18.	ITT	IDSL_AE1	Summary of All On-treatment or Post-Treatment Adverse Events Leading to Permanent Discontinuation of Study Drug or Withdrawal from Study	Footnote: All Adverse Events includes ADRs, SAEs and Non-serious AEs leading to withdrawal  Include total column	SAC [2] DRY RUN [1]

Safety: Tables					
No.	Population	IDSL / Example Shell	Title	Programming Notes	Deliverable [Priority]
3.19.	ITT	IDSL_AE1	Summary of All On-treatment or Post-Treatment Serious Adverse Events Leading to Permanent Discontinuation of Study Drug or Withdrawal from Study	Include total column	SAC [2] DRY RUN [1]
3.20.	ITT	IDSL_AE1	Summary of On-treatment or Post-Treatment Non-Serious Adverse Events Leading to Permanent Discontinuation of Study Drug or Withdrawal from Study	Include total column	SAC [2] DRY RUN [1]
3.21.	ITT	IDSL_AE1	Summary of On-treatment or Post-Treatment Adverse Drug Reactions Leading to Permanent Discontinuation of Study Drug or Withdrawal from Study	Include total column	SAC [2] DRY RUN [1]
Adverse Events of Special Interest					

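### SAP 10.3.1.3: in participants never randomised, an adverse event starting on the undefined last run-in date fails the strict run-in flag and drops out of the Not-in-ITT safety tables

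*SAP*

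**What the plan says.** SAP 10.3.1.3 assigns each AE to a phase by its start date. Run-in runs from the screening date up to, but not including, the randomisation date. On-treatment starts on the randomisation date and ends one day after the last treatment stop date. Post-treatment follows that.

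An asterisked footnote deals with people who never reach randomisation: for "participants who enter the run-in treatment phase but do not get randomised, use the last run-in date instead of randomisation date". It applies to the run-in flag and to the rule for onset time since first dose. It does not apply to the on-treatment flag, and it does not change the inequality sign.

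SAP 10.3.1 has a general default: "If it is not possible to tell whether an assessment or event was on-treatment or not, it will be considered as on-treatment".

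SAP 10.8.8 plans three AE tables for the Not-in-ITT group, all limited to run-in events:
- Table 3.3: "Overview of Run-In Treatment Non-Serious AEs leading to Withdrawal, Non-Serious ADRs and SAEs for Subjects not in ITT".
- Table 3.6: "Common (>=1%) Run-In Treatment Non-Serious Adverse Events by System Organ Class and Preferred Term (Number of Subjects and Occurrences) for Subjects not in ITT", with the note "Include total column only. Do not apply rounding".
- Table 3.15: "Summary of Run-In Treatment Serious Adverse Events by System Organ Class and Preferred Term (Number of Subjects and Occurrences) for Subjects not in ITT".

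SAP 4 assigns the Enrolled population to safety as well as to study population displays and says of it: "Included are: Run-in Failures; Randomized Participants".

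**The concern.** A strict upper bound is right when the reference is the randomisation date, because that day already belongs to the next phase. It is wrong when the reference is the last run-in date, which is itself a run-in day. The substitution removes the final day of run-in for exactly the people the footnote was written to bring in.

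These participants have taken Relvar/Breo, and Tables 3.3, 3.6 and 3.15 are the only AE summary tables that cover them. What is at stake is an undercount in those tables. Because L is undefined, two programmers who both follow the SAP could also produce different counts.

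**Working it through.** No stated figure in the plan needs reproducing. The check applies the rules literally.

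**1. The run-in flag.** The rule is: screening date ≤ AE start < reference date. For people never randomised the reference is L. Take screening on 1 January and L = 28 January as an example.

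| Participant | AE start | Run-in flag as written | With ≤ L | Onset day as written |
|---|---|---|---|---|
| Never randomised | 27 Jan (L − 1) | yes | yes | −1 |
| Never randomised | 28 Jan (L) | no | yes | +1 |
| Never randomised | 29 Jan (L + 1) | no | no | +2 |
| Randomised 29 Jan | 28 Jan | yes | – | −1 |
| Randomised 29 Jan | 29 Jan | no (on-treatment) | – | +1 |

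The same calendar day, 28 January, is run-in for the randomised participant and unassigned for the other. L < L is false whatever L means. If run-in starts and ends on the screening date, the window is empty.

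**2. Other routes into a table.**
- On-treatment needs a randomisation date, and the footnote supplies no substitute there.
- The 10.3.1 default sends unclear events to on-treatment, but every on-treatment AE table in 10.8.8 is an ITT table.
- Post-treatment needs a start later than the stop date plus one day. If L is a visit late enough to qualify, the post-treatment tables are also ITT only.

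**3. Tables affected per event.** A serious AE on L is missing from 3.3 and 3.15. A non-serious AE on L is missing from 3.3, and from 3.6 if its term would have reached 1%. At most two of the three tables lose any one event.

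**4. Size.** Protocol 5.2 says "Approximately 600 subjects will be screened to achieve 432 randomised". Planned participants not randomised: 600 − 432 = 168. This includes screen failures, who took no study drug, and the SAP does not state the Not-in-ITT denominator N. If the participant has no other qualifying event in the same row, one omission lowers a Table 3.3 percentage by 1/N:
- N = 168: 1/168 = 0.60 points
- N = 100 (assumed): 1.0 point
- N = 50 (assumed): 2.0 points

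For Table 3.6, 1/100 = 1.00% would be shown and 1/101 = 0.99% would not; 2/168 = 1.19% would. For N from 101 to 168 a term in a single participant is below the cut-off even with the sign corrected. Table 3.15 has no cut-off.

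**5. A withdrawal AE on the day of the first dose, day d.** Protocol 3.3.1 describes a supervised first dose and, for paradoxical bronchospasm, immediate discontinuation and withdrawal from the study. If L is the stop or withdrawal date, L = d, d < d is false, and the event is omitted. If L is a later early-withdrawal visit, L = d + k with k ≥ 1, d < d + k is true, and the event is kept.

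**The case against.** The strongest case against is about consequence. The rule costs one calendar day. The usual way to fail run-in is an ACT score of 20 or more at Visits 2, 3 and 4 (Protocol 5.1). Those people leave because their asthma is controlled, so an AE would have to start on their last day by chance. Protocol 6.4 names only SAEs among the AE data to be collected for run-in failures. The schedule of activities does collect non-serious ADRs and withdrawal AEs from the start of run-in, so the non-serious content is uncertain. The figure of 168 is loose: the 600 is approximate, includes screen failures, and rescreened people receive new numbers.

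Other outputs still carry the information. Listing 15 covers all AEs in people outside ITT with no phase limit. Listing 44 shows deaths. Table 1.3 and Listings 2 and 20 may show why a person left. The 24-hour SAE reporting in Protocol 9.2.1 does not use this flag.

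All of that stands, and it keeps the point small. It does not answer the inequality, which fails for an AE on L under every reading.

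A reader might infer that AEs causing withdrawal, such as bronchospasm at the first dose, will be systematically lost. The documents do not support that. Protocol 5.1 and 8.2 direct withdrawing participants to an early-withdrawal visit, so a later L is plausible, and on that reading the event is counted.

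**Conclusion.** The rule is wrong as written, and the severity is minor. For a participant who enters run-in and is not randomised, an AE starting on L is not flagged run-in and is left out of the run-in tables identified above. That conclusion rests only on the SAP text and needs no assumption about what L means.

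The number of events is unknown and probably very small. The percentage effects depend on an N that the SAP does not give. The firmest case is an SAE starting exactly on L, because SAE collection in run-in failures is explicit.

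Two wider inferences should be resisted. The event does not vanish from the report, because Listing 15 retains it. The primary comparison and all other randomised comparisons are untouched, because the affected people were never allocated to an arm.

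**What to change.** Amend the footnote in SAP 10.3.1.3 for participants who enter run-in and are not randomised:

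1. Define L, for example as the later of the last run-in Relvar/Breo stop date and the last run-in or withdrawal visit.
2. Use L + 1 as the reference date in both rules that the footnote governs. The run-in flag then becomes screening date ≤ AE start < L + 1, which is AE start ≤ L. For an AE on L the onset day becomes L − (L + 1) = −1, in line with run-in. Changing the sign in the flag alone would leave that AE flagged run-in but with onset day +1.
3. State that the run-in flag takes precedence over the post-treatment flag for these participants. With L defined as the later of two dates, an AE after stop + 1 and on or before L would otherwise meet both.

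The cost is one definition, one reference date and one sentence of precedence in the SAP, with matching programming. No new data and no protocol change are needed.

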## 10.4. Appendix 4: Data Display Standards & Handling Conventions

### 10.4.1. Reporting Process

Software	

 
The currently supported versions of SAS software will be used.
 
	
Reporting Area	
HARP Server	uksal1x00175
HARP Compound	arenv/arprod/gw685698_gw642444/mid207040/final_01
Analysis Datasets	

 
Analysis datasets will be created according to CDISC standards (SDTM IG Version 3.2 & ADaM IG Version 1.0). If the Study Data Standardization Plan (SDSP) exists for a study, ensure the CDISC versions are consistent.
 
	
Generation of RTF Files	

 
Rich Text Format (RTF) files will be generated for final reporting effort.
 
	

### 10.4.2. Reporting Standards

General		

 
The current GSK Integrated Data Standards Library (IDSL) will be applied for reporting, unless otherwise stated (IDSL Standards Location: https://spope.gsk.com/sites/IDSLLibrary/SitePages/Home.aspx):           
 
4.03 to 4.23: General Principles
 
5.01 to 5.08: Principles Related to Data Listings
 
6.01 to 6.11: Principles Related to Summary Tables
 
7.01 to 7.13: Principles Related to Graphics
 
 
 
		
All data displays (Tables, Figures & Listings) will use the term "Subject" which reflects CDISC and GSK Data Display Standards terminology		
Formats		

 
GSK IDSL Statistical Principles (5.03 & 6.06.3) for decimal places (DP's) will be adopted for reporting of data based on the raw data collected, unless otherwise stated.
 
Numeric data will be reported at the precision collected on the eCRF.
 
The reported precision from non eCRF sources will follow the IDSL statistical principles but may be adjusted to a clinically interpretable number of DP's.
 
All data will be reported according to the treatment the participant was randomised to unless otherwise stated.
 
Numeric data will be reported (in listings) at the precision collected in the eCRF or recorded in the raw dataset if from non-eCRF sources.
 
		
Specification of Number of Decimal Places for Descriptive Statistics		
Label	Description	Number of decimal places (dp) more than raw data
N	Number of participants in the treatment group	Always present to 0 dp
n	Number of participants with non-missing values	Always present to 0 dp
Mean	Arithmetic Mean	1 dp

SD	Standard Deviation	2 dp		
Median	Median	1 dp		
Min.	Minimum	0 dp		
Max.	Maximum	0 dp		
Specification of Number of Decimal Places for Statistical Analysis				
Label	Description	Number of decimal places (dp) more than raw data		
LS Mean	Adjusted mean for the treatment group	1 dp		
LS Mean Change	Adjusted mean change from baseline for the treatment group	1 dp		
Std Err	Standard error	2 dp		
Difference	Treatment difference	1 dp		
Odds Ratio	Treatment odds ratio	Always present to 2 dp		
Relative Risk	Treatment relative risk	Always present to 2 dp		
95% CI	95% Confidence interval around difference/ratio/relative risk	Same number of dp as the difference/ratio/relative risk		
p-value	p-value	Always present to 3 dp (or <0.001 or >0.999)		
Planned and Actual Time				

 
Reporting for tables, figures and formal statistical analyses: 
 
Planned time relative to treatment dosing will be used in figures, summaries, statistical analyses and calculation of any derived parameters, unless otherwise stated.
 
 
 
Reporting for Data Listings: 
 
Planned and actual time relative to study drug dosing will be shown in listings (Refer to IDSL Statistical Principle 5.05.1).
 
Unscheduled or unplanned readings will be presented within the participant's listings.
 
 
 
				
Unscheduled Visits				

 
Unscheduled visits will not be included in summary tables and/or figures.
 
All unscheduled visits will be included in listings.
 
				
Descriptive Summary Statistics				
Continuous Data	Refer to IDSL Statistical Principle 6.06.1			
Categorical Data	N, n, frequency, %			
Graphical Displays				

 
Refer to IDSL Statistical Principles 7.01 to 7.13.
 
The programs for statistical analysis tables will create SAS datasets with the unrounded numbers from the statistical models to be used in any graphs. This will include all LS means, standard errors, treatment differences or ratios and confidence intervals. This will be done for all analysis tables regardless of whether or not a figure is planned as part of statistical analysis complete (SAC).
 
The programs for all graphical displays will additionally create a CSV file with the final data that is used in the graph in order to allow the graph to be redrawn for any potential future publication requirement
 
				

## 10.5. Appendix 5: Derived and Transformed Data

### 10.5.1. General

Study Day

 
Calculated as the number of days from first randomisation: 
 
Ref Date = Missing → Study Day = Missing
 
Ref Date < Randomisation Date → Study Day = Ref Date – Randomisation Date
 
Ref Date ≥ Randomisation Date → Study Day = Ref Date – (Randomisation Date) + 1
 
 
 

Change from Baseline

 
Calculated as the difference between the value of the endpoint at the timepoint of interest and the baseline value as defined in Section 5.2 Baseline Definitions
 

Time Since First Dose

 
Calculated as the number of days from first dose date of post randomisation treatment: 
 
Ref Date = Missing → Time Since First Dose = Missing
 
Ref Date < Randomisation Date → Time Since First Dose = Ref Date – Randomisation Date
 
Ref Date ≥ Randomisation Date → Time Since First Dose = Ref Date – (Randomisation Date) + 1
 
 
 

Study Treatment Start and Stop Dates

 
In this study, participants who permanently discontinue Relvar/Breo study treatment, any sensors or the App may continue in the study attending the remaining visits and completing the scheduled assessments.
 
Data displays will state if pre-screening, run-in treatment, on-treatment, post-treatment, or both on-treatment and post-treatment data are included in the summary or analysis, when applicable. On-treatment is defined as Relvar/Breo study treatment from the date of randomisation to treatment arm.
 
Relvar/Breo on-treatment start date will be defined as the randomisation date and Relvar/Breo Treatment Stop Date will be defined as the latest treatment stop date (from the study treatment compliance eCRF log and treatment discontinuation eCRF page). These dates will be used to determine whether a measurement is run-in, on or post-treatment. (See Section 10.3.1 Study Phases).
 

Multiple Measurements at One Analysis Time Point

 
PEF and FeNO assessments are performed multiple times per visit. The maximum value obtained at the visit will be included in summaries of these data.
 

